7.3 Statistical Inference (Hypothesis)

No formal hypothesis will be tested in this observational study. The aim of the study is to describe the management of patients receiving lipid-modifying therapy. The sample size is expected to enable sufficiently precise estimates of the primary outcome measures to be obtained for each participating country.

8. Research Question and Objectives

Research Question: How are EU patients requiring lipid-modifying therapy routinely managed?

8.1 Primary Objective

To estimate the proportion of subjects in EU primary and secondary care, with or without established ASCVD and receiving LMT, with LDL-C above 2016 Joint ESC Guideline-recommended levels.

8.2 Secondary Objective

To assess clinical characteristics and management of subjects in EU primary and secondary care, with or without established vascular/atherosclerotic disease and receiving LMT.

8.3 Exploratory

Describe patient reported outcome (PRO) score related to self-management of condition (PRO data will be assessed at enrolment, where PROs are able to be implemented as part of an observational study)

9. Research Methods

9.1 Study Design

The study is a multicountry, cross-sectional, observational study of routine clinical management of European patients in primary and secondary care, who may be at elevated risk of cardiovascular event. The cross-sectional design is appropriate to provide a contemporary landscape assessment of the clinical management of this patient population.

All data will be collected at the time of the clinic visit. The subject is considered to have been enrolled when written informed consent has been obtained (if required by local practice), eligibility has been confirmed and subject data entry into the eCRF has begun.

The study electronic database (InForm) is built and provided to sites by Imperial College Trials Unit (ICTU).

There are no formal visits or assessments required as part of the study, although subjects will be invited to complete the PAM 13 questionnaire ([Appendix F](#)) if permitted by local practice to do so as part of an observational study. The questionnaire will be self-administered by the subject on a device provided to the site, and subject responses will be downloaded remotely to be scored by the PRO provider (Insignia Health). If a subject is unable or unwilling to complete the PAM 13, the remainder of the subject's study data will still be analysed as normal.

This is a non-interventional, observational study and is not intended to alter the clinical management of patients.

It is intended that at least half of the subjects enrolled will be classified as primary prevention patients, ie, are without established ASCVD. The remainder will be classified as secondary prevention patients (as evidenced by a diagnosis of established ASCVD prior to enrolment).

Enrolment will not be formally stratified by clinical characteristics; site selection (secondary vs primary care physicians) and site enrolment caps will be employed to facilitate enrolment of the required proportion of primary and secondary prevention subjects.

In addition, being cognisant of the paucity of data available on patients with a history of PVD and IS as compared to MI, the optimal enrolment ratio of MI:PVD:IS subjects is 1:2:2. This ratio will be sought by selection of appropriate specialist sites (see [Section 9.2.2](#) below).

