9.2 Setting and Study Population

9.2.1 Study Period

At the study level, data spanning the period February 2016 to December 2017 is expected to be captured.

At the individual subject level, data will be captured for up to 14 months (for LDL-C measurement) prior to and including the visit date, and include historical data on previous relevant medical history.

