9.2.3 Subject Eligibility

Inclusion Criteria

- LDL-C measurement within 14 months of enrolment, obtained independently of participation in a clinical trial
- Use of any LMT (may include statin/ezetimibe/fibrate/PCSK9 inhibitor/bile acid absorption inhibitor/nicotinic acid/other) at time of enrolment, or any LMT prescribed within 12 months prior to date of enrolment, or any LMT prescribed at date of enrolment
- Age \geq 18 years at enrolment
- Provided informed consent/notified according to local requirements
- Subject expected to survive for at least 1 year after enrolment

Exclusion Criteria

- Diagnosis of FH and with history of CV event
- Currently receiving therapy for carcinoma (excepting squamous epithelial cell)
- Known HIV positive status
- Pregnant or breastfeeding at time of enrolment
- Participating in an interventional clinical trial within 6 months prior to enrolment

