9.3 Variables

Individual site characteristics:

- Primary care/ secondary care/ speciality
- Number of patients with each relevant study indication seen per year
- Number of patients with each relevant study indication who are prescribed LMT during the conduct of the study
- Lipid guidelines followed at site (and if Yes then which ones)
- Previous/current experience of lipid-lowering RCT conduct

Subject level:

- Referral to study physician (eg referred from specialist or GP, and date referred)
- Demographics (gender, age at enrolment, ethnicity if permitted to record)
- Relevant medical history (CV events including dates, known risk factors [smoking, family history], diabetic/hypertension/renal/rheumatoid arthritis status, vascular bed involvement)
- Participation in a clinical study within previous 12 months
- Height/weight/BP/waist circumference
- Lipid profile (including fasting status) (total cholesterol, LDL, HDL, non-HDL, triglycerides, Lp(a), apo B100, apo A1), HbA1c, plasma glucose (including fasting status)
- LMT (type, dose, dose frequency, duration of prescription) at enrolment; in 12 months prior to enrolment, up to and including enrolment date
- History of intolerance to higher doses than currently, or to other statins
- Reason for prescription if non-ASCVD (eg diabetic, CKD, subject request)
- Other concomitant therapies of interest (antihypertensives, antidiabetics, antiplatelets, acetylsalicylic acid)

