9.3.2 Outcome Assessment

Primary Outcome Measure:

LDL-C measurement most recent to enrolment (within previous 14 months)

Secondary Outcome Measures:

- Lipid levels (total cholesterol, non-HDL-C, HDL, triglycerides, Lp(a), apo B100, apo A1) most recent to enrolment (within previous 14 months)
- Use of LMT (type, dose, frequency) including combination therapy, in 12 months prior to enrolment, up to and including enrolment date
- Clinical characteristics at time of enrolment as assessed in relation to:
 - FH status (diagnosed/ not diagnosed)
 - CV history (see [Appendix B](#) for a list of diagnoses/events)
 - Diabetic status (diabetic/not diabetic; Type 1 or Type II)
 - CKD status (stage, if applicable)
 - CV Risk scores

Exploratory Outcome Measure:

PAM 13 score

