9.7.2.4 Analysis of the Primary, Secondary and Exploratory Outcome Measures

9.7.2.4.1 Analysis of Primary Outcome Measure

Summaries displaying the frequency and percentage with 95% confidence interval will be presented for LDL-C within or above the 2016 Joint ESC Guideline-recommended targets. Subjects will be presented overall and split into subgroups with and without established ASCVD.

Subjects included in the secondary prevention cohort will fulfil the following:

- Documented history of MI or revascularisation (peripheral, carotid or coronary), ischaemic stroke, or symptomatic PVD, as defined in [Appendix B](#), except for patients diagnosed with familial hypercholesterolaemia (FH).
- Subjects without a history of MI or revascularisation are eligible if they have DOCUMENTED angiographic evidence of atherosclerosis defined as $\geq 30\%$ stenosis in at least one coronary artery using either standard coronary angiography or CT coronary angiography.

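### Secondary-prevention status is set by a diagnosis before enrolment, but the analysed LDL-C may be up to 14 months older, and no rule requires it to follow that diagnosis

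*Protocol*

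**What the plan says.** **Cohort status.** Section 9.1 describes the subjects who are not primary prevention as "classified as secondary prevention patients (as evidenced by a diagnosis of established ASCVD prior to enrolment". For the analysis, Section 9.7.2.4.1 requires "Documented history of MI or revascularisation (peripheral, carotid or coronary), ischaemic stroke, or symptomatic PVD, as defined in" Appendix B, or documented coronary stenosis on angiography. Neither section gives a minimum time since diagnosis or refers to the date of the LDL-C.

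**Outcome.** Section 9.3.2 names the primary outcome measure as "LDL-C measurement most recent to enrolment (within previous 14 months". The inclusion criterion in Section 9.2.3 is "LDL-C measurement within 14 months of enrolment, obtained independently of participation in a clinical trial". Section 9.2.1 states the same window: "data will be captured for up to 14 months (for LDL-C measurement) prior to and including the visit date".

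**Primary analysis.** Section 9.7.2.4.1 compares LDL-C with the guideline level, and "Subjects will be presented overall and split into subgroups with and without established ASCVD".

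**Dates available.** Section 9.3 lists among the subject-level variables "Relevant medical history (CV events including dates, known risk factors". The protocol gives these dates no part in lining up LDL-C with ASCVD status.

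**Bias statement.** Section 9.9.1.1 does not expect information bias for the primary objective, because an LDL-C value in the window is a condition of entry.

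**The concern.** The secondary-prevention proportion will be read as the share of patients with established ASCVD whose LDL-C is above the guideline level. That reading needs the LDL-C to have been drawn after ASCVD was known. Under the protocol, a first MI, ischaemic stroke, revascularisation or PVD diagnosis may fall between the last LDL-C and enrolment. The subject is then secondary prevention by history, while the LDL-C reflects management before the diagnosis.

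Such a value says nothing about how established ASCVD was treated. Yet the study is meant to estimate the gap between guidelines and practice (Section 7). If pre-diagnosis values exceed the secondary-prevention target more often than later ones, the gap is overstated. The error is systematic, so a larger sample does not reduce it.

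The reasoning in Section 9.9.1.1 shows only that a value exists for every subject. It does not show that the value belongs to the disease state under which it is judged. Section 9.9.2, which discusses limits to interpretation, does not mention the point either.

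**Working it through.** **1. The plan's own figures.** Table 2 (Section 9.5) gives 95% CI half-widths at an assumed 50%. With half-width = 1.96 × √(0.25/n) × 100:

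| n | Table 2 | Recomputed |
|---|---|---|
| 70 | 11.7 | 11.71 |
| 100 | 9.8 | 9.80 |
| 130 | 8.6 | 8.60 |
| 150 | 8.0 | 8.00 |
| 200 | 6.9 | 6.93 |
| 250 | 6.2 | 6.20 |
| 300 | 5.7 | 5.66 |

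All seven agree. The point does not depend on this table, which serves only as a yardstick.

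**2. Pooled yardstick.** About 6000 subjects are planned (Section 9.5), at least half of them primary prevention (Section 9.1). That leaves at most about 3000 in secondary prevention: 1.96 × √(0.25/3000) × 100 = 1.79 points. With fewer subjects the half-width is larger.

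**3. Who is affected.** A subject must meet both conditions:
- the first qualifying diagnosis falls in the 14 months before enrolment;
- there is no LDL-C between that diagnosis and enrolment.

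**4. Bias formula.** Let g be the share of the secondary-prevention cohort so affected. Let p_pre and p_post be the proportions above the secondary-prevention target for values drawn before and after diagnosis.

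Reported proportion = (1 − g) × p_post + g × p_pre, so bias = g × (p_pre − p_post).

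**5. Numbers.** The documents give neither g nor the difference. Assumed: p_post = 50% and p_pre = 60% to 90%, a difference of 10 to 40 points.

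| g | Difference 10 | 20 | 30 | 40 |
|---|---|---|---|---|
| 2% | 0.2 | 0.4 | 0.6 | 0.8 |
| 5% | 0.5 | 1.0 | 1.5 | 2.0 |
| 10% | 1.0 | 2.0 | 3.0 | 4.0 |

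Example: 0.05 × (90 − 50) = 2.0 points.

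**6. When it matters.** The bias equals the pooled half-width at g = 1.789 / difference, which is 17.9%, 8.9%, 6.0% and 4.5% for differences of 10, 20, 30 and 40 points.

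**7. Country level.** For prevention cohorts of 70 to 150 within a country, Table 2 gives half-widths of 11.7 to 8.0 points. The largest bias in the grid, 4.0 points, is half of the smallest of these.

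**The case against.** **An alignment rule could be left to the analysis plan.** Event dates are collected, so a SAP could add one. That is fair. But the protocol itself sets both time points and then states that information bias is not expected, which gives the author of a SAP no reason to look for the problem. The statement in Section 9.9.1.1 needs correcting in any case.

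**The enrolment-date wording is not in the primary analysis section.** The sentence in Section 9.1 belongs to a description of the intended enrolment mix, and "Clinical characteristics at time of enrolment as assessed in relation to" in Section 9.3.2 sits under the secondary outcome measures. This is true. Even so, the analysis definition in Section 9.7.2.4.1 asks only for documented history, with no timing, so the mismatch is permitted there too.

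**The most-recent-value rule narrows the group.** This stands. Any LDL-C after diagnosis replaces the earlier one, and Section 9.9.4 expects close follow-up. The affected share may be small.

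**Stronger readings that the documents do not support.**
- A reader might infer that recruiting PVD and stroke patients through specialist sites makes recent diagnoses common. Sections 9.1 and 9.2.2 seek patients with such a history and say nothing about recency.
- A reader might infer that comparisons of MI with PVD or stroke are distorted. The primary analysis names no such comparison, Section 9.7.2.4.2 offers only descriptive subgroups by clinical characteristics, and no difference in timing between these groups is shown.
- A reader might infer that affected subjects belong in the primary-prevention cohort. They have ASCVD at enrolment, so moving them would depart from Section 9.1.

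**Some mismatch would remain.** An LDL-C drawn at or just after an event still reflects earlier management. LMT first prescribed at enrolment (Section 9.2.3) raises a separate timing question in both cohorts. The fix below addresses neither.

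**Conclusion.** The point holds in limited form. As written, the protocol places pre-diagnosis LDL-C values in the secondary-prevention estimate for subjects first diagnosed inside the window and not measured since. Its dismissal of information bias does not cover this.

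The size is unknown. Under the assumed differences, the overstatement ranges from 0.2 points (g = 2%, difference 10) to 4.0 points (g = 10%, difference 40). It can therefore exceed the pooled nominal half-width of about 1.8 points, but only if g is moderately large or the difference is wide. Up to g = 10% it stays below sampling error in single-country cohorts. The upward direction is itself an assumption: with p_pre below p_post the sign reverses.

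The study is not invalidated. A headline split is misaligned for an uncounted group that could be counted wherever the dates are recorded.

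**What to change.** In Section 9.7.2.4.1:
- Use the recorded CV event dates to flag secondary-prevention subjects whose first qualifying diagnosis follows the analysed LDL-C.
- Report their number in a separate row, 'LDL-C before diagnosis'.
- Give the secondary-prevention proportion with and without them, keeping them out of the primary-prevention cohort.
- Report subjects whose qualifying diagnosis has no date as 'order unknown'. Claudication and angiographic stenosis are the likeliest cases.

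In Section 9.9.1.1, state that the entry criterion secures the availability of LDL-C but not its timing relative to diagnosis, and refer to the new row. That section also says that the two most recent values are used, while Section 9.3.2 names one. The two must be reconciled so that the flag refers to a defined LDL-C date.

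The cost is one derived variable, a few lines of text and one table row. The downside is a small group whose order cannot be determined. In return, the affected share is reported wherever both dates exist.

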9.2 Setting and Study Population

9.2.1 Study Period

At the study level, data spanning the period February 2016 to December 2017 is expected to be captured.

At the individual subject level, data will be captured for up to 14 months (for LDL-C measurement) prior to and including the visit date, and include historical data on previous relevant medical history.

9.2.2 Selection and Number of Sites

Site selection:

- Will be carried out according to normal feasibility and selection processes
- Will evaluate both primary and secondary care sites:
- At least 25% of sites will be primary care
- Secondary care sites will be selected proportionately according to speciality, to enable enrolment of a study population enriched for PVD and IS subjects
- Will require sites to demonstrate the ability to provide adequate study data ie, demographics and CV history, at least one LDL within the pre-specified window, and the previous/current LMT regimen

Selection is based on interest in participation as a study site, and willingness and ability to meet the criteria above, and to comply with the protocol and data entry conventions.

It is expected that approximately 160 sites will be selected, across approximately 18 EU countries.

9.2.3 Subject Eligibility

Inclusion Criteria

- LDL-C measurement within 14 months of enrolment, obtained independently of participation in a clinical trial
- Use of any LMT (may include statin/ezetimibe/fibrate/PCSK9 inhibitor/bile acid absorption inhibitor/nicotinic acid/other) at time of enrolment, or any LMT prescribed within 12 months prior to date of enrolment, or any LMT prescribed at date of enrolment
- Age \geq 18 years at enrolment
- Provided informed consent/notified according to local requirements
- Subject expected to survive for at least 1 year after enrolment

Exclusion Criteria

- Diagnosis of FH and with history of CV event
- Currently receiving therapy for carcinoma (excepting squamous epithelial cell)
- Known HIV positive status
- Pregnant or breastfeeding at time of enrolment
- Participating in an interventional clinical trial within 6 months prior to enrolment

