9.9 Limitations of the Research Methods

9.9.1 Internal Validity of Study Design

9.9.1.1 Information Bias

For the primary objective, information bias is not anticipated to be applicable, as having an LDL-C measurement within the 14 months preceding enrolment is an Inclusion criterion; if several measurements are available then the two most recent to enrolment will be reported and used in the study analysis.

For the secondary objectives, LMT use is an Inclusion criterion so reliable prescription details will be known and reported by the Investigator. It is also expected that Investigators will be well aware of variables concerning the secondary objectives around clinical characteristics and other laboratory values, as typically these are well documented and the subjects will be known to the Investigators.

Information bias may arise in recording reasons for LMT regimen change and/or history of statin intolerance, as these are more liable to be subjective and based on individual judgement; accurate and truthful reporting is encouraged in the eCRF through provision of a range of pre-populated response options and a free text field for Investigator comments. Interpretation of these objectives should take these factors into account.

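### The primary LDL-C value need not have been drawn on lipid-modifying therapy (LMT), so pre-treatment values of new starters can count as above target in subjects described as receiving LMT

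*Protocol*

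**What the plan says.** The primary objective (Protocol 8.1) is a proportion among subjects "with or without established ASCVD and receiving LMT, with LDL-C above 2016 Joint ESC Guideline-recommended levels".

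Eligibility (9.2.3) has two relevant parts. The LDL-C criterion is "LDL-C measurement within 14 months of enrolment, obtained independently of participation in a clinical trial". The LMT criterion can be met in three ways: use at enrolment, "or any LMT prescribed within 12 months prior to date of enrolment, or any LMT prescribed at date of enrolment".

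The primary outcome measure (9.3.2) is "LDL-C measurement most recent to enrolment (within previous 14 months"). The primary analysis (9.7.2.4.1) is a frequency and percentage with a 95% confidence interval: "Subjects will be presented overall and split into subgroups with and without established ASCVD". It states no restriction to values drawn on treatment.

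On bias, 9.9.1.1 says "For the primary objective, information bias is not anticipated to be applicable", because an LDL-C measurement in the window is an inclusion criterion. The same sentence adds that "if several measurements are available then the two most recent to enrolment will be reported and used in the study analysis", which does not match the single latest value in 9.3.2.

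The LMT data listed in 9.3 are "LMT (type, dose, dose frequency, duration of prescription) at enrolment; in 12 months prior to enrolment, up to and including enrolment date".

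**The concern.** The objective describes control under treatment, but the eligibility and outcome rules are not tied to each other in time. The LMT criterion looks at prescribing up to and including the enrolment day. The LDL-C criterion looks back 14 months. No section asks whether LMT was in use when the blood was drawn.

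The clearest case is the subject whose first LMT prescription is written on the enrolment day. Section 9.1 requires no study assessments, so the latest LDL-C on file is a pre-treatment value, quite possibly the one that prompted the prescription. Under the plan it enters the primary proportion as a value in a subject receiving LMT.

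The study is meant to quantify the gap between guidelines and practice and to inform policy (section 7). Pre-treatment values widen that gap for a reason unrelated to how well treated patients are controlled, and a larger sample does not reduce the effect. If the share of new starters differs between countries or between primary and secondary care, comparisons across them are affected too. That is plausible, but the protocol does not document it.

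**Working it through.** **Which subjects can contribute an off-LMT value under the rules as written**

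- First-ever LMT prescription on the enrolment day: eligible under the third route. The latest LDL-C is pre-treatment.
- LMT started within the previous 12 months: eligible. The latest LDL-C may predate the start, because any value from the previous 14 months is accepted.
- LMT prescribed within the previous 12 months and since stopped: eligible under the second route. The latest LDL-C may postdate the stop, or may have been drawn on treatment. Only the post-stop value is an off-LMT value.

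If the two latest values are used, as 9.9.1.1 says, the older one is more likely to predate LMT.

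**The plan's own precision figures**

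Table 2 (9.5) uses 50%. Half-width = 100 × 1.96 × √(0.25/n):

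- n = 70, 100, 130, 150, 200, 250, 300 gives 11.71, 9.80, 8.60, 8.00, 6.93, 6.20, 5.66 points. All seven match the table to one decimal.
- n = 6000 (planned total) gives 1.27 points.
- n = 3000 (half the total, since 9.1 intends at least half to be primary prevention) gives 1.79 points.

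These figures cover sampling error only.

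**Shift from off-LMT values**

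Let f be the share of analysed LDL-C values drawn off LMT, and p_on and p_off the proportions above target on and off LMT. The reported proportion is (1 − f) × p_on + f × p_off, so

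bias = f × (p_off − p_on).

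The protocol gives none of the three inputs as an expected value. I take p_on = 50% from the precision assumption in 9.5; f and p_off are my assumptions. Bias in percentage points:

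| f | p_off 70% | p_off 80% | p_off 90% | p_off 95% |
|---|---|---|---|---|
| 5% | 1.0 | 1.5 | 2.0 | 2.25 |
| 10% | 2.0 | 3.0 | 4.0 | 4.5 |
| 20% | 4.0 | 6.0 | 8.0 | 9.0 |

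**Share at which the bias equals the half-width** (p_on 50%, p_off 80%, so f = half-width / 30)

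- n = 6000: 1.27 / 30 = 4.2%
- n = 3000: 1.79 / 30 = 6.0%
- n = 200: 6.93 / 30 = 23.1%

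**Sensitivity to p_on**

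With p_on = 70%, f = 10% and p_off = 80-95%, the bias is 0.10 × 10 = 1.0 to 0.10 × 25 = 2.5 points, against 3.0 to 4.5 with p_on = 50%.

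**The case against.** The strongest reply is that the protocol often describes a population prescribed LMT rather than one exposed to it at a given moment. The rationale (7.2), the description of subjects (9.7.2.3.2) and external validity (9.9.2) all use the language of prescription. On that reading, a patient who was prescribed LMT, stopped it and is above target belongs to the gap the study wants to measure. This stands in part for discontinuers. It does not rescue the new starter: an LDL-C drawn before any LMT was prescribed cannot show how LMT is working, on either reading.

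Second, the magnitude is assumed throughout. The 50% in 9.5 was chosen because it gives the widest interval, not as a forecast, and most subjects may be long-term users. This stands. A reader might infer that the headline result is wrong by several points, or that country estimates are swamped. The protocol supports neither, because it gives no off-LMT share, and at n = 200 the share would have to be large.

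Third, a reader might infer that the cure is to analyse only subjects on a stable regimen. That goes too far. Patients whose drug or dose was recently changed are receiving LMT, and some were probably changed because LDL-C was high, so excluding them could bias the proportion downward.

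Fourth, an SAP could restrict the analysis to on-treatment values, and 9.7.2.5 allows sensitivity analyses by clinical characteristics. That is true, but eligibility, the outcome definition and the statement in 9.9.1.1 are protocol text. The limitation disclosed in 9.9.2 concerns a different group, patients with no recent LDL-C.

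**Conclusion.** The point holds. Followed exactly, the eligibility and outcome rules let pre-treatment LDL-C values of new starters, and post-stop values of some discontinuers, into a proportion described as applying to subjects receiving LMT. Since LMT lowers LDL-C, the expected direction is upward. Discontinuers whose last value was drawn on LMT do not inflate it.

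The size cannot be determined from the protocol. As an illustration, +3.0 to +4.5 points follows from f = 10%, p_on = 50% and p_off = 80-95%, all assumed. With p_off = 80%, a share of about 4% would match the sampling error of the overall estimate (1.3 points at n = 6000), while about 23% would be needed in a country of 200. The practical exposure is therefore mainly in the overall result and the results by ASCVD status.

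The statement in 9.9.1.1 is wrong as reasoned. Requiring an LDL-C value ensures that it exists, not that it was drawn on treatment.

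**What to change.** Keep the eligibility criteria and change the analysis definition:

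1. Base the primary proportion on subjects whose analysed LDL-C was drawn after LMT start and while LMT was prescribed. Do not require an unchanged regimen.
2. Report separately the subjects whose value is pre-LMT, post-stop or unclassifiable. The last group needs a stated rule for LDL-C from months 12-14, because LMT use is collected over 12 months and the listed prescription duration may not reach back further.
3. Give the all-enrolled proportion as a sensitivity analysis, so the prescribed-population reading is also served.
4. Confirm that the eCRF captures the LDL-C sampling date and LMT start and stop dates. Section 9.3 lists duration of prescription but names none of these dates, so it should not be assumed that they are already there.
5. Correct 9.9.1.1, and reconcile its two LDL-C values with the single value in 9.3.2.

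The cost is protocol and SAP wording, a derived on-LMT status and possibly added date fields. The primary set becomes somewhat smaller. If, as an assumption, 20% of a 200-subject country were lost, n = 160 gives 100 × 1.96 × √(0.25/160) = 7.7 points instead of 6.9.
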